## 2. OBJECTIVE

The objectives of this study are to determine by repetitive epidermal contact, the primary or cumulative irritation and the allergic contact sensitization potential of the ColActive Plus Collagen Matrix Dressing, under maximized conditions, with controlled product quantity and application site. The data will be used as part of a regulatory submission to the FDA.

# 3. QUALITY REVIEW AND VERIFICATION

This study will be conducted in adherence to Good Clinical Practice Regulations (21 CFR 50: Protection of Human Subjects-Informed Consent). These procedures are designed to ensure adherence to the spirit of Good Clinical Practices (GCPs), as described in:

- International Council for Harmonization (ICH) of Technical Requirements for Pharmaceuticals for Human Use, ICH Harmonized Tripartite Guidelines for Good Clinical Practice 2023 [ICH E6 (R3)].
- US 21 CFR dealing with clinical studies (including part 50 concerning informed consent).
- Declaration of Helsinki, concerning medical research in humans (Recommendations Guiding Physicians in Biomedical Research Involving Human Subjects, Helsinki 1964, amended Tokyo 1975, Venice 1983, Hong Kong 1989, Somerset West 1996, Edinburgh 2000, Washington 2002, Tokyo 2004, Seoul 2008, and Brazil 2013).

The Investigator agrees when signing the protocol to adhere to the instructions and procedures described in it and, thereby, to adhere to the GCPs to which it conforms. The study data and final report will be reviewed and signed by Quality Assurance staff. The Investigator will permit trial related monitoring, audits and regulatory inspections and will provide copies of, and direct access to, source data/documents.

# 4. BACKGROUND 

Allergic contact dermatitis (sensitization) results when a substance contacting the skin has undergone an immunological alteration in its reactivity. This altered reactivity is the result of prior exposure of the material to the skin, which may lead to the hallmark visual symptoms of erythema, edema, papules.

Primary (acute) irritation is a complex biologic syndrome, with a diverse pathophysiology, natural history and clinical appearance. When exposure is sufficient and the offending agent/test material is potent, classic symptoms of acute skin irritation are seen which include hallmark visual symptoms of erythema, edema, and papules. The irritant reaction quickly peaks and then begins to heal upon removal of irritant. The onset is acute and often after one single exposure. Predictive testing is widely performed to determine the irritant potential of test agents.

This procedure is used as a predictive test for contact sensitization in humans. The procedure involves the application of a discontinuous series of occlusive patches to human skin over a three-week induction period. Induction is followed by an approximate two-week rest period. Challenge consists of a single application to naive skin.

### 5. TEST PRODUCT

ColActive Plus Collagen Matrix Dressing is an advanced wound dressing made from fish-derived collagen, sodium alginate, carboxymethylcellulose (CMC), and ethylenediaminetetraacetic acid (EDTA). ColActive Plus is a topically applied wound dressing that will transform into a soft gel sheet when in contact with wound exudates.

An adequate amount of test article will be supplied by the Sponsor in containers suitable for use by the testing facility. Enough test products will be supplied to last for the maximum number of subjects for the entire study duration. Responsibility of the identity, purity, strength, safety, composition, and stability of the test articles will remain with the Sponsor. Additionally, by signing this protocol the Sponsor confirms that the test articles being evaluated are composed of common cosmetic ingredients with a known, favorable, safety profile and do not pose a

known health risk when used as intended. The test articles will be stored in a secured location with the temperature monitored until use.

Upon arrival at ALS the test product will be assigned a unique laboratory code number and entered into a daily log identifying the lot number, sample description, sponsor, date received, and tests requested.

Sample will be retained for a minimum of 30 days beyond submission of final report. Sample disposition will be conducted in compliance with appropriate federal, state and local ordinances.

# 6. SUBJECT SELECTION CRITERIA

Approximately 75 healthy subjects satisfying all criteria listed below will be enrolled to complete the study with a minimum of 50 subjects.

## 6.1 Inclusion Criteria

Individuals included in the study will be enrolled based upon the following criteria.

- 1. Age: 18-70
- 2. Sex: Male & Female
- 3. Fitzpatrick: I-V, minimum 10% of panel Fitzpatrick V.
- 4. Individuals who will be able to read, understand and give an informed consent relating to the study they are participating in.
- 5. Individuals who will be free of any dermatological or systemic disorder, which in the Investigator's opinion, could interfere with the study results.
- 6. Individuals who will be in general good health and who will complete a preliminary medical history form mandated by the testing facility.
- 7. Individuals who will be able to and agree to cooperate with the Investigator and clinical staff.
- 8. Individuals who will agree to have test products applied in accordance with the protocol and are able to complete the full course of the study.
- 9. Individuals who have not participated in a similar study in the past 30 days.
- 10. Individuals who agree to refrain from sun tanning/bathing and prolonged exposure to sunlight (outdoors).
- 11. Female volunteers who are willing to undergo a urine pregnancy test.
- 12. Individuals who agree to not change their current brand of personal care products such as soaps, body washes, laundry detergents, body sprays, body spritzes, etc. while participating on the study.

# 6.2 Exclusion Criteria

Individuals meeting any of the following criteria will be excluded from study participation.

- 1. Individuals who are currently taking any medications (topical or systemic) that may mask or interfere with the test results (specifically, corticosteroids, topical and/or systemic [except nasal steroids], non steroidal anti-inflammatory drugs [e.g. ibuprofen, Advil, Motrin, aspirin > 325mg/day], antihistamines, and topical/oral immunosuppressive medications). Subjects must refrain from using any topical/oral anti-inflammatory medications during the length of the study (6 weeks).
- 2. Individuals who have a history of any acute or chronic disease that might interfere with or increase the risk on study participation. (e.g., systemic lupus erythematosus, rheumatoid arthritis, HIV positive).
- 3. Individuals who are diagnosed with chronic skin allergies (atopic dermatitis/eczema) or recently treated skin cancer within the last 12 months.
- 4. Individuals who have damaged skin in close proximity to test sites (e.g., sunburn, uneven skin pigmentation, tattoos, scars, excessive hair, active acne papules or other disfigurations).
- 5. Individuals who control their diabetes using insulin.
- 6. Individuals with any history, which in the Investigator's opinion, indicates the potential for harm to the subject or places the validity of the study in jeopardy.
- 7. Female volunteers who indicate that they are pregnant or are planning to become pregnant or nursing.
- 8. Individuals with a known history of hypersensitivity to any cosmetics, personal care products, fragrances, and/or adhesives.
- 9. Employees of ALS.

10. Individuals with a known fish allergy.

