# 7. INFORMED CONSENT FORM AND MEDICAL HISTORY FORM

An informed consent will be obtained from each subject consistent with requirements in 21 CFR 50 prior to initiating the study describing reasons for the study, possible adverse effects, associated risks and potential benefits of the treatment and their limits of liability. Subjects will sign and date the informed consent document to indicate their authorization to proceed and acknowledge their understanding of the contents. Each subject will be sent home with a signed and dated copy of the informed consent form. Each subject will be assigned a subject identification number and medical history information will be collected. This information, along with the signed consent forms will be available for inspection on the premises of ALS only.

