#### 9.4 Test Product Preparation

Test Product Preparation will be performed as noted below unless otherwise requested by Sponsor. Prepare ColActive Plus Collagen Matrix Dressing samples using the following method:

Step 1: ColActive Plus Collagen Matrix Dressing: cut with sterile scissors to fit the chamber of the patch (25-millimeter diameter).
Step 2: Place the test article directly on the Hill Top Chamber®.
Step 3: 0.8mL of distilled water will be dispensed to saturate the test product.\*

Step 4: Place a Hill Top Chamber® on the test site.

\*Visual inspection will be done to confirm the entire test article has come in contact with distilled water and test product has transformed into a gel.

9.5 Test Sites/ Procedure:

The patches will be applied directly to the skin of the intrascapular regions of the back, to the right and/or left of the midline, and/or upper arms.

Subjects will be given a Panelist Instructions for the Safety Patch Test. Subjects will be dismissed with instructions to keep the test area dry while the patches are in place and to not expose the test area to direct sunlight. Subjects will be instructed to notify clinical staff during the course of the study should they begin using any new medications, cease taking any medications or have any change in their medical condition.

Patches will remain in place for a minimum of 48 hours. Subjects will be instructed to not remove the patches prior to their next scheduled visit. Subjects patched on Friday will have patches remain on until the following Monday (72 hours). The procedure will be repeated until a series of 9 consecutive 48-hour exposures have been made over 3 consecutive weeks. This is considered the induction phase.

Before each re-application, the test sites will be visually evaluated for any reaction.

Following the induction phase, subject will be given a minimum of 10-day rest period.

A challenge or test dose will be applied once to a previously unexposed test site. Clinical staff will remove the patches 48 hours post-application. Reactions will be scored 30 minutes post-removal, 24-hours post-removal, and 48-hours post-removal. The skin grader will be blinded to the treatment assignments and any previous scores.

Skin response to the test product will be evaluated according to the Berger and Bowman Scale (Section 8. Experimental Techniques and Methods).

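### Exclusion 1 names drugs that may mask skin reactions but bars only current use, with no drug-free interval before the first patch, the reading on which irritation is reported

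*Protocol*

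**What the plan says.** Protocol section 6.2, exclusion 1, removes "Individuals who are currently taking any medications (topical or systemic) that may mask or interfere with the test results". It names corticosteroids (nasal ones excepted), NSAIDs (with aspirin counted above 325 mg/day), antihistamines and immunosuppressives. Its next sentence looks forward: "Subjects must refrain from using any topical/oral anti-inflammatory medications during the length of the study (6 weeks".

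The other visible medication rules also concern the study period. Appendix I, question 11, asks for a commitment to abstain for the six weeks and extends it to antihistamines and immunosuppressives. Section 9.5 tells subjects to "notify clinical staff during the course of the study should they begin using any new medications". Section 10 allows removal for incompatible concomitant treatments.

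Two general provisions can reach earlier drug use. Exclusion 6 lets the Investigator exclude anyone whose history "places the validity of the study in jeopardy". Section 7 says that "medical history information will be collected", and inclusion 6 requires that each person "will complete a preliminary medical history form mandated by the testing facility".

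Elsewhere the criteria do look back. Inclusion 9 admits "Individuals who have not participated in a similar study in the past 30 days", and exclusion 3 uses 12 months for treated skin cancer.

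Section 14 takes the irritation result from the scores after the first 48-hour patch and the sensitization result from the challenge phase.

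**The concern.** The protocol itself gives masking as its reason for excluding these drugs. That reason does not end with the last dose, but the exclusion does. Someone who finished a short course a day or two before the first patch is not clearly taking the drug at enrolment, and can keep the on-study commitment without difficulty.

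What is at stake is the irritation result. Of all the scheduled readings, the one chosen for it lies closest to any pre-study dose. If a drug still dampens the skin response at that point, the error runs toward finding no irritation, which is the favourable direction in a safety study meant for a regulatory submission. With no interval stated, two similar volunteers could also be handled differently.

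**Working it through.** The protocol gives no figure to reproduce here. The check has two parts: whether any visible rule reaches recent past use, and how far each reading lies from a last pre-study dose.

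**Rules, by the period that they cover**

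| Provision | Period covered |
|---|---|
| 6.2, exclusion 1, first sentence | Current use |
| 6.2, exclusion 1, second sentence | The 6 study weeks |
| Appendix I, question 11 | The 6 study weeks |
| 9.5, reporting of medication changes | During the study |
| 10, incompatible concomitant treatments | During the study |
| 6.2, exclusion 6 | Any history, by Investigator opinion, no interval |
| 7, medical history | Collected, no drug-free rule attached |

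Exclusion 2 and inclusion 5 would remove many people treated for a disease, but they turn on the disease or disorder, not on the drug. For an otherwise healthy recent user, exclusion 6 is what remains.

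**Timeline**

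Inputs from section 9.5: nine induction patches over three weeks, each worn 48 hours, or 72 hours when applied on a Friday; then "subject will be given a minimum of 10-day rest period"; then one challenge patch removed at 48 hours and scored 30 minutes, 24 hours and 48 hours after removal. Assumptions: Induction 1 is applied on a Monday (day 0), the last dose is taken the day before (day −1), and the rest period is the 10-day minimum.

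- Induction readings fall on days 2, 4, 7, 9, 11, 14, 16, 18 and 21.
- Gap from last dose = reading day + 1, giving 3, 5, 8, 10, 12, 15, 17, 19 and 22 days.
- Challenge is applied on day 21 + 10 = 31, removed on day 31 + 2 = 33, and read on days 33, 34 and 35. The gaps are 34, 35 and 36 days.
- If Induction 1 is applied on a Friday, the first patch comes off on day 3 and the first gap is 4 days instead of 3.
- A longer rest period only lengthens the challenge gaps.

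The first reading, which carries the irritation result, thus comes 3 to 4 days after such a dose, and the challenge readings come at least 34 days after it.

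**Effect of a look-back**

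If a subject must be drug-free for L days before Induction 1, the gap to the first reading is at least L + 2 days. For L = 7 this is 9 days; for L = 30 it is 32 days.

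How long each drug class dampens a skin reaction, and how many recent users would enrol, are not in the protocol. The timeline therefore shows which reading is exposed, not by how much.

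**The case against.** The best reply is that exclusion 1 is clear and consistent with the rest of the protocol, and that leaving a recent user to the Investigator is a deliberate choice of the kind also made in inclusion 5. Exclusion 6 fits such a person directly, and medical history is taken from everyone. This stands in part: the protocol does have a route to exclusion. It does not tell the Investigator what interval matters, although the criteria give explicit look-backs for other matters.

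A second reply is that the forms may already ask. This also stands. The numbering of Appendix I goes from 7d to 10 in the text at hand, and the medical history form is not shown. A reader might infer that recent use is never asked about; the document does not support that. What can be said is that no visible rule states a disqualifying interval.

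A third reply is that the study has other safeguards. Eight later induction readings follow the first, all responses are tabulated, and the 0.5% SLS control at Induction 1 shows each subject's reactivity at the very reading in question. These limit the harm. They do not remove it, because section 14 rests the irritation result on the first patch, and section 9.3 states no action for a subject who fails to react to SLS, whereas a reaction to the negative control leads to removal.

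Finally, the size is unknown and any interval proposed is an assumption. That is correct, and it determines the weight given below.

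**Conclusion.** The point holds as a modest weakness in an eligibility rule. Exclusion 1 identifies drugs that may mask results, bars only their current use, and leaves a healthy recent user to unguided judgement, while the irritation result comes from the most exposed reading, about 3 days after a last dose taken the day before (Monday start).

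Any bias would run toward no reaction. Its size cannot be derived from the protocol and is probably small. One could suppose that some fraction of the roughly 75 enrolled or 50 completing subjects is fully masked and compute a loss of sensitivity, but nothing in the protocol supports a fraction or complete masking, so such a figure would not be evidence of magnitude. The protocol also states no reaction-rate limit against which to judge it.

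A reader might go further and infer that the sensitization result is compromised or the study invalid. The text does not support either. The challenge readings lie at least 34 days after a last pre-study dose, and the later induction readings lie 5 to 22 days after it. Severity is low: this is a cheap improvement.

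**What to change.** Amend exclusion 1 to cover people who are currently taking, or have taken within a stated interval before Induction 1, any of the listed drugs. The Investigator should set the intervals by drug class, and they should be fixed in the protocol before enrolment. As a starting point, and as assumptions only: 30 days for non-nasal corticosteroids and immunosuppressives, and 7 days for NSAIDs and antihistamines. The 30 days merely matches the length of the look-back in inclusion 9, which concerns prior study participation and not drug clearance. Keep the present exceptions for nasal steroids and aspirin up to 325 mg/day.

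Add a recent-use question to Appendix I, with a yes answer making the person ineligible, unless the items not shown already ask it. Keep question 11 as the on-study commitment.

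The cost is a change of wording, at most one form question, and a few extra screen failures, mainly among users of common NSAIDs and antihistamines. Most of these can be rescheduled once the interval has passed.

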# 7. INFORMED CONSENT FORM AND MEDICAL HISTORY FORM

An informed consent will be obtained from each subject consistent with requirements in 21 CFR 50 prior to initiating the study describing reasons for the study, possible adverse effects, associated risks and potential benefits of the treatment and their limits of liability. Subjects will sign and date the informed consent document to indicate their authorization to proceed and acknowledge their understanding of the contents. Each subject will be sent home with a signed and dated copy of the informed consent form. Each subject will be assigned a subject identification number and medical history information will be collected. This information, along with the signed consent forms will be available for inspection on the premises of ALS only.

# 8. EXPERIMENTAL TECHNIQUES AND METHODS

Skin response to the test product will be evaluated according to the Berger and Bowman Scale listed below.

#### Induction Phase (Berger and Bowman1 Scale)

## Numeric Scores

- 0 = No evidence of irritation
- 1 = Minimal erythema, barely perceptible
- 2 = Moderate erythema, readily visible; or minimal edema; or minimal papular

response

- 3 = Strong erythema; or erythema and papules
- 4 = Definite edema
- 5 = Erythema, edema and papules
- 6 =Vesicular eruption
- 7 = Strong reaction spreading beyond test site

## Letter Grades (always upper case)

- A = Slight glazed appearance
- B = Marked glazing
- C = Glazing with peeling and cracking
- F = Glazing with fissures
- G = Film of dried serous exudate covering all or a portion of the patch site
- H = Small petechial erosions and/or scabs

## **Challenge Phase**

### **Inflammatory Responses**

- 0 =No visible reaction
- + = Slight, confluent or patchy erythema
- 1 = Mild erythema (pink)
- 2 = Moderate erythema (definite redness)
- 3 = Strong erythema (very intense redness)

Definition of letter grades appended to a numerical grade:

- E = Edema swelling, spongy feeling when palpated
- P = Papule red, solid, pinpoint elevation
- V = Vesicle small elevation containing fluid
- B = Bulla reaction fluid-filled lesion (blister)
- S = Spreading evidence of the reaction beyond the Webril® pad area
- W = Weeping result of a vesicular or bulla reaction serous exudate
- I = Induration solid, elevated, hardened, thickened skin

## **Superficial Effects**

g = Glazing

# y = Peeling

- c = Scab, dried film of serous exudate of vesicular or bulla reaction
- d = Hyperpigmentation (reddish-brown discoloration of test site)
- h = Hypopigmentation (loss of visible pigmentation at test site)
- f = Fissuring grooves in the superficial layers of the skin

Each of the scores represents the presence of a clinically significant effect that is localized in a representative portion of the patch area, defined as 25% or more of the patch site. Questionable (barely perceptible, minimal or involving less than 25% of the patch site) reactions as well as the + designation are inconclusive and are not included in calculation.

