The Sponsor will be notified within 1-2 business days of any subject who: •exhibits an erythema score of 2 or greater •exhibits papules, vesicles, bullae and/or spreading beyond the patch site, regardless of the degree of erythema •requires follow-up

If any subject exhibits a grade 2 during induction phase, the test site will be changed. If the subject shows another grade 2 of the same test product during induction phase at the new test site, the test product will be discontinued for safety concerns. If any subject shows a grade 3 or greater during induction phase, the test site will be discontinued for safety concerns.

If any subject shows a significant reaction at the 30 minutes post-removal, 24-hours post-removal, or 48-hours post-removal evaluation during the challenge phase (Grade 1, 2, and 3 only), the Investigator may decide to schedule a re-challenge patch test for confirmatory purposes. This follow-up investigation will be conducted approximately 4-8 weeks after the completion of the challenge phase and will be identical to the challenge phase.

In the event of a re-challenge patch the original test substance should be applied under the same testing conditions (concentration and patch type) to confirm delayed contact hyper-reactivity. Related substances (product reformulations, individual ingredients, ingredient groups, etc.) can also be applied to aid in determining the causative relationship but must be pre-approved prior to application.

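### Does the unlabelled exclusion of questionable reactions in Protocol Section 8 remove the mildest induction grades from the irritation result?

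*Protocol*

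**What the plan says.** Protocol Section 8 sets out two scales under separate headings.

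- **Induction**, headed as the Berger and Bowman scale: numeric grades 0 to 7 plus letter grades. The two lowest non-zero grades are "1 = Minimal erythema, barely perceptible" and "2 = Moderate erythema, readily visible; or minimal edema; or minimal papular" response.
- **Challenge**: 0, +, 1, 2 and 3, with appended letters and a list of superficial effects. The + entry is defined as "Slight, confluent or patchy erythema", and grade 1 is mild, pink erythema.

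After the superficial effects, two sentences close the section. The first says that each score stands for a clinically significant effect over at least a quarter of the patch site. The second is the exclusion: "Questionable (barely perceptible, minimal or involving less than 25% of the patch site) reactions as well as the + designation are inconclusive". It ends by saying that these reactions "are inconclusive and are not included in calculation".

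Three other places bear on the point.

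- Sections 8 and 9.5 both state "Skin response to the test product will be evaluated according to the Berger and Bowman" scale. Section 8 adds that the scale is listed below; Section 9.5 adds a cross-reference to Section 8.
- Section 9.5 states "If any subject exhibits a grade 2 during induction phase, the test site will be changed". It also allows a re-challenge after a significant challenge reaction, limited to grades 1, 2 and 3.
- Section 14 reports irritation from the scores after the first 48-hour patch removal, and puts each subject's skin responses in a table.

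**The concern.** The exclusion carries no phase label, and its descriptive words seem borrowed from the wrong scale. *Barely perceptible* and *minimal* nearly repeat the definition of induction grade 1, and *minimal* recurs in induction grade 2. No challenge entry uses either word. Taken literally, the rule would make induction grade 1 and some grade 2 scores inconclusive.

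Irritation is one of the two stated objectives, and its result comes from an induction reading. If grade 1 dropped out, two analysts could report different irritation summaries and each could cite the protocol. The literal reading would also sit awkwardly with Section 9.5, which acts on every induction grade 2.

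The naming of the scales adds to the doubt. If the Berger and Bowman scale were also used at challenge, a grade 1 there would be inconclusive under Section 8, yet could count as a significant reaction under Section 9.5.

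**Working it through.** The protocol gives no figure to reproduce here, so the check is mainly a comparison of texts.

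**Step 1. Where the words occur.** The two terms were looked up in every grade definition of both scales.

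| Term | Induction (14 entries) | Challenge (18 entries) |
|---|---|---|
| *barely perceptible* | grade 1 | none |
| *minimal* | grades 1 and 2 | none |
| + symbol | not on the scale | on the scale |
| 25% area criterion | in no grade definition | in no grade definition |

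The word match is therefore real: 2 of the 7 non-zero induction grades (grade 2 by 2 of its 3 routes) against 0 of the 4 non-zero challenge entries. The third row points the other way, because the same sentence names a symbol that only the challenge scale has.

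**Step 2. Position.** The induction block ends with its letter grades. The Challenge Phase heading follows, then the inflammatory responses, appended letters and superficial effects, then the exclusion. No heading returns the reader to induction.

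**Step 3. Meaning of the excluded class.** The sentence before the exclusion treats every score as a clinically significant effect of sufficient area. Beside it, *questionable* describes a response too faint or too small to earn a score. An assigned induction grade 1 is a score. Voiding it would leave the induction scale with a lowest non-zero grade that could never count.

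**Step 4. Which scale at challenge.** Section 8 attaches the Berger and Bowman name to the induction heading. Section 9.5 uses that name but refers back to Section 8, where challenge has its own scale. The re-challenge provision lists grades 1, 2 and 3, which are all the numeric non-zero grades on the challenge scale but fewer than half of the 7 on Berger and Bowman. On the challenge scale grade 1 is mild erythema, so the clash over grade 1 does not arise.

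**Step 5. Induction grade 2.** Section 9.5 governs what happens to the test site; Section 8 governs what enters a calculation. A score can trigger the first and be left out of the second without contradiction.

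**Step 6. Size under each reading.** On the challenge-only reading, the change in any irritation summary is 0. The other reading can only be sized with assumed counts, because the protocol gives none. Take 50 subjects (the minimum in Section 6), with half of the grade 2 scores reached through minimal edema or papules.

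- *5 with grade 1 and 2 with grade 2*
  - All counted: mean (5 + 2×2)/50 = 0.18, with 7 reactors.
  - Excluded scores set to 0: 2×1/50 = 0.04.
  - Excluded scores dropped: 2/(50 − 5 − 1) = 2/44 = 0.045.
  - Either exclusion leaves 1 reactor.
- *20 with grade 1 and 4 with grade 2*
  - All counted: mean (20 + 2×4)/50 = 0.56, with 24 reactors.
  - Excluded scores set to 0: 2×2/50 = 0.08.
  - Excluded scores dropped: 4/(50 − 20 − 2) = 4/28 = 0.143.
  - Either exclusion leaves 2 reactors.

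The strained reading would matter if anyone adopted it and if such a summary were produced. The conclusion therefore rests on Steps 2 to 4, not on the effect being small under both readings.

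**The case for a change.** The strongest case for a change is that the protocol itself fixes this rule, so an analysis plan cannot be relied on to settle it. The defining words belong to induction, and the Berger and Bowman name appears in Section 9.5 directly after the challenge readings. Section 9.3 also grades the negative control on Berger and Bowman and applies it throughout the study, which includes challenge. The data are meant for a regulatory submission, and a clarification costs only wording.

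Part of this stands. The sentence has no phase label, the borrowed words match no listed challenge grade, and the scale name is used loosely, including for the negative control. None of it changes how the test product's scores are counted. The control wording concerns a different site and does not move the exclusion out of the challenge block. Nor would a phase label alone finish the tidying, because *minimal* and *barely perceptible* would still correspond to no challenge entry. They make sense only as descriptions of a response below the scoring threshold, which is how the sentence already reads in its place.

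**Conclusion.** The textual observation is correct, but it does not call for a change. The exclusion belongs to the challenge block by position and by its use of +. On that reading every induction grade stays in, no grade is both inconclusive and significant, and the effect on the irritation result is 0. This is a labelling slip that a competent analyst resolves from the page.

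The conclusion rests on two assumptions: that test sites at challenge are graded on the challenge scale in Section 8, and that the table required by Section 14 shows the scores as recorded. With that table, a reader could rebuild an irritation summary under either reading. The protocol defines no irritation mean or reactor rate. Any such summary may be specified in an analysis plan that is not at hand, so its absence here is no fault. If the protocol is amended for other reasons, a phase label and consistent scale names would be a courtesy to the reader.
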